9.2.10 End-of-Study Drug Treatment Visit

Subjects are to return to the study site within 3 days after the subject's last dose of study drug to complete all end-of-study drug treatment assessments as described below. This may occur at the visit at which disease progression is diagnosed.

- Complete physical examination, including weight
- Vital sign measurements (sitting blood pressure, pulse, respiratory rate, temperature)
- ECOG Performance status

-
- Leptomeningeal metastasis symptom assessment – Cohort B only.
 - Hematology, serum chemistry, and urinalysis
 - Urine pregnancy test, if applicable (positive results to be confirmed by serum pregnancy testing)
 - Supine 12-Lead ECG (repeat three times consecutively within 30 minutes [must have an interval of at least 1-2 minutes between ECGs])
 - Tumor assessment (brain MRI, thoracic and abdominal CT/MRI) (only required if one hasn't been performed in the previous 8 weeks)
 - Quality of Life Questionnaire
 - Concomitant medications
 - AE assessment
 - Final return and accounting of study drug

9.2.11 30-Day Follow-Up

The 30-Day Follow-Up should occur 30 days (\pm 5 days) after the subjects' last dose of tesevatinib, but prior to starting new therapy. This may occur prior to 30 days if new therapy is started within 30 days of last dose of study drug.

- Complete physical examination, including weight
- Vital sign measurements (sitting blood pressure, pulse, respiratory rate, temperature)
- ECOG Performance status
- Hematology, serum chemistry, and urinalysis
- Urine pregnancy test, if applicable (positive results to be confirmed by serum pregnancy testing)
- Concomitant medications
- AE assessment

9.2.12 Follow-Up Phone Contact

Beginning 8 weeks after the 30-Day Follow-Up Visit, subjects are to be contacted by telephone every 8 weeks to assess survival status and any subsequent anti-cancer treatment.

9.2.13 Unscheduled/AE Resolution Visits: To Occur as Needed

If additional visits are needed (e.g. for resolution of an AE), the following procedures and evaluations may be performed as needed:

- Complete physical examination, including weight;
- Vital sign measurements (sitting blood pressure, pulse, respiratory rate, temperature);
- ECOG Performance status

- Hematology, serum chemistry and urinalysis;
- Urine pregnancy test, if applicable (positive results to be confirmed by serum pregnancy testing);
- Supine 12-Lead ECG (repeat three times consecutively within 30 minutes [must have an interval of at least 1-2 minutes between ECGs];
- Tesevatinib administration (if appropriate)
- AE assessment;
- Concomitant medications;
- Perform drug accountability, review subject diary, and collect old and dispense new study drug (if appropriate).

10 REMOVING SUBJECTS FROM STUDY

Every reasonable effort will be made to keep the subject in the study; however, in the event that a subject is withdrawn from the study, every effort will be made by the investigator to complete and report the reasons for withdrawal as thoroughly as possible. The reason for termination must be clearly documented on the appropriate page of the eCRF. Study withdrawal should include the final assessments, as required by the protocol and every effort should be made to perform the study follow-up procedures (e.g. laboratory tests, physical examination including an evaluation of toxicity/AEs). Refer to Table 4-1 and Table 4-2.

A termination eCRF must be completed for all enrolled subjects.

10.1 Subject Withdrawal

A subject's participation in the study may be prematurely discontinued for any of the following reasons:

10.1.1 Subject Treatment Discontinuation

- Progression of disease
- An AE requires permanent discontinuation of study drug
- Voluntary withdrawal by subject
- Noncompliance to protocol
- Subject lost to follow-up
- Termination of the study by sponsor
- Subject death
- Other

10.1.2 Subject Study Termination

- Voluntary withdrawal by subject
- Subject lost to follow-up
- Termination of the study by sponsor
- Subject death
- Other

In the event of premature discontinuation, every effort should be made to perform the end-of-study follow-up procedures. Refer to Table 4-1 and Table 4-2. If a subject dies, Kadmon will actively seek to know the date of death.

Subjects who are withdrawn from the study due to toxicity are to be followed until there is either:

- Resolution or stabilization to Cycle 1 Day 1 or Grade 1
- The subject is lost to follow-up
- The event is otherwise explained

If there is an ongoing toxicity associated with tesevatinib, subjects must be followed with appropriate medical management until resolution or stabilization.

A reasonable effort should be made to contact any subject who is lost to follow-up during the course of the study in order to complete assessments and retrieve any outstanding data. If a subject is unreachable by telephone after three (3) attempts, the minimum of a registered letter should be sent requesting that the subject make contact with the investigator.

Once a subject discontinues from the study for any reason, every effort will be made to collect all clinical and laboratory data as scheduled for the End-of-Study (Final) visit (see Section 9.2.9).

10.2 Study Discontinuation

Kadmon Corporation has the right to terminate or to stop the study at any time. Reasons for study discontinuation may include, but are not limited to the following:

- The incidence or severity of AEs in this or other studies evaluating the drug indicates a potential health hazard to subjects;
- Subject enrollment is unsatisfactory;
- Drug supply issues;
- Data recording is inaccurate or incomplete;
- Excessive subject self-withdrawal;
- Significant protocol deviations (e.g. violation of eligibility criteria, dosing errors, missing data for study endpoint analysis).

10.3 Replacements

Subjects discontinued from the trial will not be replaced.

11 STUDY DRUG

11.1 Tesevatinib (KD019)

Tesevatinib will be provided in 100-, and 150-mg tablets. Kadmon will provide each investigator with adequate supplies of tesevatinib. Study drug must be stored at controlled room temperature and inventoried according to applicable regulations.

Subjects will be provided with either a weekly or monthly supply of study drug and instructions for taking the study drug at home. After the initial 28-day cycle, study drug will be supplied on Day 1 of each subsequent cycle to those continuing on study. Unused drug must be returned to the study site at each visit for accounting and reconciliation.

Tesevatinib tablets are white to off-white round tablets that contain API in a lactose-based immediate release (IR) formulation. Tesevatinib tablets are packaged in high-density polyethylene (HDPE) bottles capped with childproof caps. The following information will be printed on the label for clinical lots of tesevatinib:

Tesevatinib Tablets 100-mg – 32 count

Lot Number: XXXXX.XXX Bottle #: XXXX

Store at 20°C - 25°C (68°F - 77°F). Brief excursions permitted to 15°C to 30°C (59°F and 86°F)

Caution: New Drug--Limited by Federal (or United States) Law to Investigational Use

Tesevatinib Tablets 150-mg – 32 count

Lot Number: XXXXX.XXX Bottle #: XXXX

Store at 20°C - 25°C (68°F - 77°F). Brief excursions permitted to 15°C to 30°C (59°F and 86°F)

Caution: New Drug--Limited by Federal (or United States) Law to Investigational Use

11.1.1 Tesevatinib Administration

Tesevatinib will be administered at the dose of 300 mg once daily. One cycle will be defined as 28 days of treatment.

Study drug may be taken with or without food at approximately the same time every morning (unless there is a patient-specific rationale to take it regularly at a different time of day). Subjects should drink a full glass of water (approximately 8 ounces [240 mL]) immediately after study drug administration. Grapefruit and similar (pomelo fruit, Seville oranges, etc.) products should be avoided for the duration of study treatment.

Subjects must be instructed not to make up missed doses unless the missed dose can be taken within 12 hours of the normal dosing time. Subjects should not re-take study drug doses in the event of vomiting.

Subjects will be treated with study drug until disease progression or unacceptable toxicity occurs. However, subjects with limited peripheral disease progression (oligoprogressive disease) may receive local ablative (radiation therapy or surgery) and then be continued on tesevatinib. Subjects who discontinue tesevatinib treatment will be followed for survival. (Both CNS and non-CNS disease progression are defined in Appendices A and B.)

All subjects also will be followed for a period of 30 days following their last dose of tesevatinib. Additionally, subjects will be contacted every 8 weeks to collect information on survival and other therapies.

11.1.2 Dose Modifications and Delays for Toxicity Related to Study Drug

Subjects who develop \geq Grade 3 AE considered by the investigator to be related to study drug (with the exception of asymptomatic Grade 3 elevations of amylase or lipase, Grade 3 elevation of alkaline phosphatase in a subject known to have bone metastases, Grade 3 elevation of glucose in a subject receiving systemic corticosteroids, Grade 3 creatine phosphokinase [CPK] elevation in the absence of muscle symptoms, or Grade 3 sodium values \geq 126 mmol/L in a subject with diarrhea) will have study treatment interrupted until all drug-related toxicities have resolved to \leq Grade 1.

Tesevatinib will be withheld for any Grade 3 rash or diarrhea related toxicities. Once toxicities have resolved to \leq Grade 1, the subject may resume study treatment at a reduced dose of 250 mg/day if the dose was 300 mg/day, or at a reduced dose of 200 mg/day if the dose was 250 mg/day. No more than two dose reductions are permitted. Subjects who require more than two dose reductions will have study drug discontinued and enter the Follow-up Period.

Subjects for whom toxicity persists beyond 28 days despite dose interruption may resume study treatment only with permission from the responsible medical monitor.

If study treatment is withheld, the subject should be instructed not to make up the withheld doses.

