11.1.3 Tesevatinib: Warnings, Precautions, and Management

AEs that have been associated with tesevatinib include the following: diarrhea, skin rash, QTc(F) prolongation, elevated serum creatinine, elevated serum amylase and interstitial lung disease.

Unless otherwise specified, study drug may be withheld for up to 28 days at the discretion of the investigator.

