11.1.3.1 Diarrhea

Diarrhea should be managed according to accepted practice (e.g. with loperamide). Subjects with severe diarrhea who are unresponsive to loperamide or other antidiarrheals or who become dehydrated may require interruption of study drug until resolution to \leq Grade 1 in severity. If Grade 3 diarrhea occurs, the medical monitor should be consulted about study drug decreases or discontinuation. In the event of severe or persistent diarrhea, nausea, anorexia, or vomiting associated with dehydration, study drug should be discontinued, and appropriate measures should be taken to rehydrate the subject intensively via intravenous fluid administration. In addition, renal function and serum electrolytes, including potassium and magnesium, should be monitored in subjects at risk of dehydration.

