11.1.3.2 Skin Rash

Skin rash should be managed according to locally accepted clinical recommendations. Study drug may be withheld up to 28 days for Grade 3 rash.

Suggestions for Rash Management (Lacouture 2011, Kiyohara 2013, www.psoriasis.org)

Papulopustular (acneiform) rash:

- Most common rash seen with EGFR inhibitors
- Typically seen in the first few weeks of treatment
- Usually peaks at Week 4–6
- Then will decrease in severity at Week 6–8
- Post-inflammatory skin changes can last for months, so prevention and reactive treatment are important

Suggestions for preventative treatment:

- Subject education prior to starting treatment on what to expect
- Gentle cleansing of skin using mild soap products
- Use of moisturizer twice daily making sure to include hands, feet and nails
- Avoid sun when possible and use of sunscreen SPF 30 or higher (preferably titanium dioxide or zinc oxide)
- Hypoallergenic makeup when possible

Suggestions for treatment once a rash appears (see Appendix F for steroid potency

chart):

- Ongoing use of treatments from ‘preventative treatments’ above
- Grade 1 (<10 % BSA involved, without pruritus or tenderness)
 - Topical steroids (refer to Appendix F for a steroid potency chart that categorizes brand- name topical steroid medications)
 - For face use medium potency
 - For body use strong potency
 - **Note: As soon as rash improves the lowest strength steroid that controls rash should be used, especially on the face**
- Grade 2 (10%–30% BSA involved, ± pruritus/tenderness; limiting instrumental ADLs and causing psychosocial impact)
 - Topical steroids
 - For face use strong potency
 - For body use very strong potency
 - **Note: As soon as rash improves the lowest strength steroid that controls rash should be used, especially on the face**
 - Systemic treatment
 - Doxycycline 100 mg BID (less renal toxic than minocycline, but can cause photosensitivity)
- Grade 3 (> 30% BSA involved, limiting ADLs)
 - Refer to dermatology
 - Topical steroids
 - All areas very strong potency
 - **Note: As soon as rash improves the lowest strength steroid that controls rash should be used, especially on the face**
 - Systemic treatment
 - Doxycycline 100 mg BID
 - Oral steroids: prednisolone 10 mg once daily (QD) for 1 week or equivalent

Suggestions for once a rash reappears:

- Over the course of treatment rash may come and go
 - Hydrocortisone 1% cream with moisturizer and sunscreen twice daily, in combination with doxycycline 100mg bid

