 - May need to follow guidelines above if rash worsens

If unacceptable rash recurs on reintroduction of tesevatinib at the same dose, then dose reduction of tesevatinib should be discussed with the medical monitor.

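### For Grade 3 rash, Protocol 11.1.2 and 11.1.3.2 differ on the hold and the restart dose, and 11.1.3.1 gives two instructions for severe diarrhea with dehydration; the protocol does not say which governs.

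*Protocol*

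**What the plan says.** **Rash.** Section 11.1.2 states: "Tesevatinib will be withheld for any Grade 3 rash or diarrhea related toxicities". Once toxicity is back to Grade 1 or less, "the subject may resume study treatment at a reduced dose of 250 mg/day if the dose was 300 mg/day", or at 200 mg/day if the dose was 250. No other restart dose is named for these events. The Safety assessments row of the synopsis also requires a hold for at least possibly related events of Grade 3 or higher. Rash is not among its exceptions, and it gives no restart dose.

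Section 11.1.3.2 states: "Study drug may be withheld up to 28 days for Grade 3 rash". Its only mention of dose reduction is: "If unacceptable rash recurs on reintroduction of tesevatinib at the same dose, then dose reduction of tesevatinib should be discussed" with the medical monitor.

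**Diarrhea.** Section 11.1.3.1 says that subjects with severe diarrhea who do not respond to antidiarrheals, or "who become dehydrated may require interruption of study drug until resolution" to Grade 1 or less. The next sentence sends Grade 3 diarrhea to the medical monitor for a decision on reducing or stopping drug. The sentence after that says that for severe or persistent diarrhea and related symptoms "associated with dehydration, study drug should be discontinued", and the subject rehydrated intravenously.

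**General default.** Section 11.1.3 opens with: "Unless otherwise specified, study drug may be withheld for up to 28 days at the discretion of the investigator".

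**The concern.** Rash and diarrhea are expected toxicities of this drug, and 11.1.3 is where an investigator would look when one occurs. If 11.1.3.2 is read alone, the hold for Grade 3 rash is optional, and a first restart at the same dose appears to be the normal course. If 11.1.2 is read, the hold is required and the restart is one step down. Two sites could therefore give different doses to subjects with the same event.

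For diarrhea, a subject who has severe diarrhea and becomes dehydrated meets both sentences of 11.1.3.1. One site could pause drug and another could end treatment.

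**Working it through.** The check is mainly a comparison of text. The documents state no figure to reproduce.

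**1. Grade 3 rash, side by side**

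| Question | 11.1.2 | 11.1.3.2 |
|---|---|---|
| Is the hold required? | Yes | Worded as permitted, up to 28 days |
| Restart dose | 250 mg/day after 300; 200 mg/day after 250 | None stated; the text presupposes a return at the same dose |
| When does reduction come in? | At the first restart | After unacceptable rash recurs at the same dose, by discussion |

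**2. Is there a rule of precedence?** The nearest candidate is the opening words of the 11.1.3 default. They qualify only the investigator's discretionary hold. They do not rank 11.1.2 against 11.1.3.2.

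**3. Which hold does the reintroduction sentence refer to?** The only hold that 11.1.3.2 names is the one for Grade 3 rash, so that is the most natural antecedent. The sentence itself sets no grade.

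**4. How does the protocol write a same-dose restart when it means one?** Section 11.1.3.4 allows a return to the pre-event dose when the central laboratory does not confirm the QTc(F) value, and it sets conditions. Section 11.1.2 has no such allowance for rash.

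**5. Dose difference.** Inputs are the dose levels in 11.1.2.
- First step: 300 / 250 = 1.20, so a same-dose restart is 20% above the named dose.
- Second step: 250 / 200 = 1.25, so 25% above.

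**6. Severe diarrhea with dehydration.** The first sentence in 11.1.3.1 says a pause may be needed, with an end point of Grade 1 or less. The later sentence says drug should be stopped, with no end point. Usage elsewhere does not settle the word *discontinued*. In 11.1.2 it is final, with entry into follow-up. In 11.1.3.7 it stands unqualified for suspected interstitial lung disease. In 11.1.3.4 the protocol adds *permanently* when it wants that meaning. Even if a temporary stop is meant, the two sentences differ in force.

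**The case against.** The rash passages can be reconciled. Section 11.1.2 is the dose-modification section and uses mandatory language, and the synopsis supports the mandatory hold. The 28 days in 11.1.3.2 match the point in 11.1.2 beyond which a restart needs the medical monitor's permission, so that sentence may only cap the length of the hold. The reintroduction sentence speaks of unacceptable rash, not Grade 3 rash, and it follows a list of suggestions. Section 5.1.2.4 records Grade 2 rash that polycystic kidney disease subjects did not tolerate, so a discretionary hold for rash below Grade 3 is a real case, and 11.1.2 names no restart dose for it. This reading is plausible, but the protocol does not state it. The Grade 3 hold sentence also stands before the suggestions heading, not under it.

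For diarrhea, the objection has more force. If severe is taken as Grade 3, 11.1.2 stops drug in every case, and 11.1.3.1 brings in the medical monitor on what follows. The two can be applied together. What remains is whether the stop is temporary or final.

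Four stronger readings are tempting, and the documents do not support them.
- **That 11.1.2 forbids a same-dose restart, or that 11.1.3.2 orders one after Grade 3 rash.** The first says a subject may resume at the reduced dose, and the second does not mention Grade 3 in its reintroduction sentence.
- **That a number of subjects would be misdosed.** No Grade 3 rash rate is given, and nothing shows how often a site would follow 11.1.3.2 over 11.1.2. The dose-reduction percentages reported for study XL647-203 carry no grades.
- **That treatment would run on for a set number of extra episodes.** Section 11.1.2 does set a limit ("Subjects who require more than two dose reductions will have study drug discontinued and enter the Follow-up Period"). A count would need Grade 3 rash to recur at every dose and the site to set 11.1.2 aside each time, and nothing in the documents suggests that course.
- **That the results would be biased.** The SAP plans no formal hypothesis test, Protocol 16.3.3 presents alterations in dosing, and SAP safety listing 4.2.1 lists dose modifications.

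**Conclusion.** The point holds as a minor inconsistency in dosing-safety rules. For Grade 3 rash, the two sections differ on whether the hold is required and on when the dose comes down. For severe diarrhea with dehydration, 11.1.3.1 gives two instructions and leaves the permanence of the stop unstated. The protocol does not say which text governs.

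The only supported size is the dose difference if a site restarts at the same dose: 20% above the dose 11.1.2 names at the first step and 25% at the second. This assumes the site relies on 11.1.3.2 alone. The higher dose at the first step is the protocol's own starting dose. The point has no effect on sample size, endpoints or analysis.

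**What to change.** - **Section 11.1.3:** add a sentence that 11.1.2 governs holds and restart doses for Grade 3 rash and diarrhea.
- **Section 11.1.3.2, hold:** make the Grade 3 hold mandatory, for up to 28 days, with restart at the reduced dose in 11.1.2.
- **Section 11.1.3.2, reintroduction:** limit the same-dose sentence to discretionary holds for rash below Grade 3.
- **Section 11.1.3.1:** replace the two dehydration instructions with one. Drug is interrupted until diarrhea is Grade 1 or less and the subject is rehydrated. The medical monitor and the site then decide between restart under 11.1.2 and permanent discontinuation. Keep the existing Grade 3 consultation.

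The cost is amendment wording and a site memo, with no added visits, procedures or subjects. Investigators would lose the option of reading 11.1.3.2 as allowing a same-dose restart after Grade 3 rash; 11.1.2 already names only the reduced dose.

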11.1.3 Tesevatinib: Warnings, Precautions, and Management

AEs that have been associated with tesevatinib include the following: diarrhea, skin rash, QTc(F) prolongation, elevated serum creatinine, elevated serum amylase and interstitial lung disease.

Unless otherwise specified, study drug may be withheld for up to 28 days at the discretion of the investigator.

11.1.3.1 Diarrhea

Diarrhea should be managed according to accepted practice (e.g. with loperamide). Subjects with severe diarrhea who are unresponsive to loperamide or other antidiarrheals or who become dehydrated may require interruption of study drug until resolution to \leq Grade 1 in severity. If Grade 3 diarrhea occurs, the medical monitor should be consulted about study drug decreases or discontinuation. In the event of severe or persistent diarrhea, nausea, anorexia, or vomiting associated with dehydration, study drug should be discontinued, and appropriate measures should be taken to rehydrate the subject intensively via intravenous fluid administration. In addition, renal function and serum electrolytes, including potassium and magnesium, should be monitored in subjects at risk of dehydration.

11.1.3.2 Skin Rash

Skin rash should be managed according to locally accepted clinical recommendations. Study drug may be withheld up to 28 days for Grade 3 rash.

Suggestions for Rash Management (Lacouture 2011, Kiyohara 2013, www.psoriasis.org)

Papulopustular (acneiform) rash:

- Most common rash seen with EGFR inhibitors
- Typically seen in the first few weeks of treatment
- Usually peaks at Week 4–6
- Then will decrease in severity at Week 6–8
- Post-inflammatory skin changes can last for months, so prevention and reactive treatment are important

Suggestions for preventative treatment:

- Subject education prior to starting treatment on what to expect
- Gentle cleansing of skin using mild soap products
- Use of moisturizer twice daily making sure to include hands, feet and nails
- Avoid sun when possible and use of sunscreen SPF 30 or higher (preferably titanium dioxide or zinc oxide)
- Hypoallergenic makeup when possible

Suggestions for treatment once a rash appears (see Appendix F for steroid potency

chart):

- Ongoing use of treatments from ‘preventative treatments’ above
- Grade 1 (<10 % BSA involved, without pruritus or tenderness)
 - Topical steroids (refer to Appendix F for a steroid potency chart that categorizes brand- name topical steroid medications)
 - For face use medium potency
 - For body use strong potency
 - **Note: As soon as rash improves the lowest strength steroid that controls rash should be used, especially on the face**
- Grade 2 (10%–30% BSA involved, ± pruritus/tenderness; limiting instrumental ADLs and causing psychosocial impact)
 - Topical steroids
 - For face use strong potency
 - For body use very strong potency
 - **Note: As soon as rash improves the lowest strength steroid that controls rash should be used, especially on the face**
 - Systemic treatment
 - Doxycycline 100 mg BID (less renal toxic than minocycline, but can cause photosensitivity)
- Grade 3 (> 30% BSA involved, limiting ADLs)
 - Refer to dermatology
 - Topical steroids
 - All areas very strong potency
 - **Note: As soon as rash improves the lowest strength steroid that controls rash should be used, especially on the face**
 - Systemic treatment
 - Doxycycline 100 mg BID
 - Oral steroids: prednisolone 10 mg once daily (QD) for 1 week or equivalent

Suggestions for once a rash reappears:

- Over the course of treatment rash may come and go
 - Hydrocortisone 1% cream with moisturizer and sunscreen twice daily, in combination with doxycycline 100mg bid
 - May need to follow guidelines above if rash worsens

If unacceptable rash recurs on reintroduction of tesevatinib at the same dose, then dose reduction of tesevatinib should be discussed with the medical monitor.

